Study Objective

To assess the efficacy of povidone-iodine wash before wound closure in preventing surgical site infections.

Trial Design

Superiority, parallel group randomized controlled trial, allocation 1:1

Methods

Study Setting

Operative theatres at Ain Shams University Hospitals

Inclusion Criteria

- Adult patients (≥ 18 years old)
- Open and minimally invasive surgeries
- Emergency (any unplanned admission) and elective (planned admission) surgical procedures
- Clean, Clean-Contaminated, Contaminated, Dirty wounds [22], (See appendix 1)
- Inclusion surgery list according to Current Procedural Terminology (CPT) National Healthcare Safety Network (NHSN) operative procedure code mapping [23] , List of included surgical procedures (See appendix 2)

Exclusion Criteria

- Povidone-iodine allergy
- Surgeries for infected wounds.
- Exclusion surgery list according to Current Procedural Terminology (CPT) National Healthcare Safety Network (NHSN) operative procedure code mapping, [23] List of excluded surgical procedures, (See appendix 3)

Intervention

- 10% povidone iodine wound wash before wound closure versus direct wound closure.
- Antibiotic prophylaxis will be administered according to local protocols.
- Wound dressing type and frequency will not differ between both groups.
- Diagnosed SSIs will be managed according to local antibiograms and management guidelines.

Outcomes

- Primary: Incidence of superficial and deep surgical site infection (SSI) within 30 days postoperatively
- Secondary:
 1. Post-operative morbidity and mortality by (Clavien-Dindo classification system) [24], (See appendix 4)
 2. Length of hospital stay
 3. Readmission and Reoperations related to surgical site infection
 4. Infectious complications (Sepsis, septic shock, multiple-organ dysfunction syndrome, wound dehiscence) [25-28]
 5. Microbiology culture and sensitivity results
 6. Local adverse events for povidone-iodine application (Local irritation, poor wound healing)
 7. Cost-analysis

Participant Timeline

Recruitment will start from day (18/09/2021) till sample size is reached.

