The study participants will be divided into 4 groups (Clean, Clean-contaminate, Contaminated, Dirty).

Each group will be stratified and analyzed separately.

Subgroup analyses will also be performed according to the type of surgical access (open versus minimally invasive), and the presence or absence of Diabetes.

The need for additional subgroup analyses will be determined at the time of completion of data collection.

Both per-protocol and intention to treat analyses will be used and their findings will be reported.

Monitoring

The study will not employ a data monitoring committee (DMC) as the trial is conducted on an adult population with no perceived risk to either arm of the trial.

Interim analysis will be done on reaching 50% of the total sample size by an independent statistician blinded for the intervention allocation. The unblinded data will be reported to the Ain Shams Surgical Research Group. The primary purpose of this analysis would be to determine if the study should be prematurely terminated in the case of patient harm. The final decision on the matter will reside with the Ain Shams Surgical Research Group and the study's principal investigators.

In our study an adverse event will be defined as any medical occurrence in a subject with a probable causal relation to the intervention.

Adverse events will be collected after the subject has provided consent and enrolled in the study.

The known as well as novel adverse effects of the study intervention (povidone iodine) will be investigated and recorded until the period of patient follow up is completed.

Ethics and Dissemination

Ethical Approval

This protocol, the template informed consent forms (Arabic and English versions), and any subsequent modifications will be reviewed and approved by the applicable IRB [institutional review board] with respect to scientific content and compliance with applicable research and human subjects' regulations prior to starting the study.

Protocol Amendments

Any modifications to the protocol which may impact on the conduct of the study, potential benefit of the patient or may affect patient safety, including changes of study objectives, study design, patient population, sample sizes, study procedures, or significant administrative aspects will require a formal amendment to the protocol. Such amendments will be reviewed and approved by the IRB prior to implementation in accordance with local regulations.

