Patient identification details (used locally for follow-up only)		
Patient name:	Study ID:	Phone number:
3) Follow up		

3-1 *Follow up intervals: (Make sure you contact the patient at every interval, then checkmark the interval that the patient develops SSI)
 
 0-7 days  8-14 days  15-21 days  22-28 days  28-30 days
	
3-5 *SSI survey Qs: (check all that apply) Does the patient suffer from....
 
 Pain or tenderness at the surgical site  Swelling at the surgical site  Hotness at the surgical site  Pus draining from the site of incision  Fever postoperatively (degree:)  Surgical incision has been deliberately opened by a physician for signs of infection before due time for stitch removal
 
*if the patient scored 1/6 or more please ask him to directly go to the surgical outpatient clinic to complete the follow up process.
 
*if the patient scored 0/6 please repeat the SSI survey in the mentioned intervals till the end of the 30 days follow up.
	
3-6-1 *Did the patient develop SSI within 30 days postoperatively?
 
 Yes, please specify the postoperative day:  No
 
3-6-2* Was the patient readmitted to the hospital due to SSI?
 
 Yes (for how many days:)  No
 
3-6-3* Did the SSI require another surgical procedure?
 
 Yes (specify:)  No

3-2 *Follow up was done through: (check all that applies)
 
 Inpatient hospital records  Outpatient clinic  Over phone
	
3-7 *Did the patient develop any of the following due to SSI? (check all that apply)
 
 Sepsis  Septic shock  Multiple organ dysfunction syndrome  Wound dehiscence  Others (specify)
	
3-8 *Was there any adverse effect of PVP-I application?
 
 Local skin reaction  Poor wound healing  Other: (please specify:)

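### Local wound harm is recorded only when attributed to povidone-iodine, so secondary outcome 6 has no reliable control rate

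*Protocol*

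**What the plan says.** Three places in the protocol tie local harm to the antiseptic.

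- **Monitoring:** "an adverse event will be defined as any medical occurrence in a subject with a probable causal relation to the intervention". The same section adds that "The known as well as novel adverse effects of the study intervention (povidone iodine) will be investigated and recorded" until follow-up ends.
- **Outcomes, secondary 6:** "Local adverse events for povidone-iodine application (Local irritation, poor wound healing").
- **Appendix 6, follow-up form, item 3-8:** "Was there any adverse effect of PVP-I application"? The boxes are local skin reaction, poor wound healing and other. There is no box for none.

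The control arm is closed directly, without the wash (Participant Timeline). Patients and outcome assessors are blinded, and the allocation is kept out of the regular records (Blinding). An interim analysis takes place at 50% of the sample, and its stated aim is safety: "The primary purpose of this analysis would be to determine if the study should be prematurely terminated in the case of patient harm".

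**The concern.** Local irritation and poor healing also occur after ordinary closure. Only the difference between arms shows whether the wash adds to them, so outcome 6 needs a control rate collected in the same way as the PVI rate. The wording asks for something else, namely a judgement that PVI caused the event. Taken literally, a control patient cannot qualify, and a blinded assessor cannot make the judgement at all.

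At stake is the one secondary outcome dedicated to local harm from the intervention, both in the final comparison and as one input to the interim harm review.

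**Working it through.** **Step 1. Is there another field that supplies the control rate?** The protocol gives no adverse event rate to reproduce, so the main check is textual.

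| Source | What it records in both arms | Rate of non-infective poor healing or skin reaction? |
|---|---|---|
| Item 3-5, "SSI survey Qs: (check all that apply) Does the patient suffer from" | Pain, swelling, hotness, pus, fever, incision opened by a physician | No; neither delayed healing nor redness or rash is listed |
| Item 3-7, "Did the patient develop any of the following due to SSI" | Wound dehiscence, sepsis and related events | No; limited to SSI |
| Item 3-9 | One Clavien-Dindo grade with a free-text reason | No; an event may appear in the text, but no rate follows |
| Appendix 5 | CDC criteria for SSI | No; erythema appears only inside superficial criterion c, for an incision that was opened and not tested |
| Clinic visit after week 1 | All patients are seen | Possible, but the form field for the finding is item 3-8 |
| Weekly calls afterwards | SSI symptoms; a positive answer leads to a clinic visit | Not if the wound shows no SSI symptom |

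Item 3-8 is therefore the only dedicated field. Because it has no box for none, a blank may mean no event, an event not attributed to PVI, or a question not asked.

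**Step 2. What happens if blinding holds?** The assessor does not know the arm. If everyone ignores the attribution and ticks whatever is seen, the comparison is unbiased. If doubtful events are left blank, both arms lose events.

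The size can only be illustrated. Assumed inputs are true rates of 6% (PVI) and 2% (control), half of the events recorded in each arm, and Fisher's exact test at two-sided 0.05, counting only results against PVI. The group size of 345 comes from Sample Size. The interim size is 760 / 2 / 2 = 190 per arm, or 190 × 0.9 = 171 with 10% lost to follow-up.

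Recorded rates with half recording are 0.5 × 6% = 3% and 0.5 × 2% = 1%. Power is the sum, over all pairs of counts (i, j) with i > j and Fisher p ≤ 0.05, of Bin(i; n, p₁) × Bin(j; n, p₂).

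| n per arm | All recorded (6% v 2%) | Half recorded (3% v 1%) |
|---|---|---|
| 171 (interim) | 36% | 13% |
| 190 (interim) | 41% | 16% |
| 345 (final) | 73% | 37% |

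**Step 3. What happens if someone completing the form knows the arm?** Assume equal true rates of 3% and the same test. The chance of a false signal against PVI is:

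| PVI / control events recorded | n = 171 | n = 190 | n = 345 |
|---|---|---|---|
| all / all | 1.0% | 1.1% | 1.5% |
| all / half | 6.9% | 8.2% | 19% |
| all / none (upper bound) | 41% | 51% | 95% |

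A normal approximation gives 26% in place of 19% for the all / half case at 345. The direction is the same.

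**The case against.** The strongest reply is that the design already protects the comparison. One form serves both arms, item 3-8 has no skip for controls, and a blinded assessor cannot withhold a tick because of the arm. This largely stands. The wording alone does not produce recording that differs by arm; someone must know the allocation. Data Collection Methods allows surgeons on the collection teams, but it does not say that the operating surgeon completes the follow-up of that patient.

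A reader might therefore infer that controls will have zero events and that a false harm signal is likely. The protocol does not support that. The last row of step 3 contradicts the stated blinding and is only an upper bound. Nor does the protocol say that a test on item 3-8 would stop the trial.

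A reader might also infer that the trial has no controlled harm data. That goes too far. SSI, SSI-related readmission, reoperation and sepsis, and Clavien-Dindo grade are recorded in both arms without reference to PVI. Grade I covers any departure from the normal postoperative course.

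What the reply does not remove is the gap in step 1. Outcome 6 has a usable control rate only if staff disregard the wording of the question.

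**Conclusion.** The point holds, at minor to moderate weight. The definition, outcome 6 and item 3-8 make local harm depend on an attribution that blinded assessors cannot make and that controls cannot meet. No other field gives a rate of non-infective poor healing or local skin reaction, so outcome 6 has no reliable control rate.

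With blinding intact, the expected damage is inconsistent recording or under-recording in both arms, which can hide real local harm. The fall in power from 73% to 37% shows the possible scale. It rests on assumed rates, an assumed recording fraction and an assumed test, because the protocol gives none of these. The primary outcome is not affected.

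**What to change.** - **Outcome 6:** reword it as local wound events in either arm (local irritation or skin reaction, poor wound healing).
- **Item 3-8:** remove the reference to PVP-I and offer local skin reaction, poor wound healing, other and none, with date of onset. Complete it for every patient at the week-1 visit and at each existing follow-up contact.
- **Monitoring:** drop the causality condition for these local wound events. Put any opinion on cause in a separate field.
- **Comparison:** compare incidence between arms, at the interim and at the end, for events with onset after wound closure. The protocol collects from an earlier point ("Adverse events will be collected after the subject has provided consent and enrolled in the study"), whereas the envelope is opened only just before closure, so earlier events do not belong in this comparison.

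Collecting every event of any cause from consent is not needed. Clavien-Dindo grading already measures general morbidity in both arms, and in transplant, aortic and emergency surgery the added recording would be considerable.

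The cost is one definition, one outcome line, one form item and slightly more local events to record. No new visits or staff are required.

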Class I/Clean: An uninfected operative wound in which no inflammation is encountered, and the respiratory, alimentary, genital, or uninfected urinary tract is not entered. In addition, clean wounds are primarily closed and, if necessary, drained with closed drainage. Operative incisional wounds that follow no penetrating (blunt) trauma should be included in this category if they meet the criteria.

[figure not shown]
Class II/Clean-Contaminated: An operative wound in which the respiratory, alimentary, genital, or urinary tracts are entered under controlled conditions and without unusual contamination. Specifically, operations involving the biliary tract, appendix, vagina, and oropharynx are included in this category, provided no evidence of infection or major break in a sterile technique is encountered.

Class III/Contaminated: Open, fresh, accidental wounds. In addition, operations with major breaks in a sterile technique (eg, open cardiac massage) or gross spillage from the gastrointestinal tract, and incisions in which acute or no purulent inflammation is encountered are included in this category.

Class IV/Dirty-Infected: Old traumatic wounds with retained devitalized tissue and those that involve existing clinical infection or perforated viscera. This definition suggests that the organisms causing postoperative infection were present in the operative field before the operation.

CDC = Centers for Disease Control and Prevention.

Algorithm for wound classification

(2) Included surgeries

1. Vascular surgeries

- a) **Abdominal aortic aneurysm repair** (Resection of abdominal aorta with anastomosis or replacement)
- b) **Limb amputation** (Total or partial amputation or disarticulation of the upper or lower limbs, including digits)
- c) **Shunt for dialysis**
- d) **Carotid endarterectomy** (Thromboendarterectomy, including patch graft, Reoperation, carotid, thromboendarterectomy, more than 1 month after original operation)

2. Hepatobiliary surgeries

- a) **Bile duct, liver, and pancreatic surgery** (Excision of bile ducts or operative procedures on the biliary tract, liver, or pancreas)
- b) **Gallbladder surgery** (Cholecystectomy and cholecystostomy)
- c) **Liver transplant**

3. Gastrointestinal surgeries

- a) **Appendectomy**
- b) **Intestinal resection and anastomosis**
- c) **Segmental colectomies** (Incision, resection, or anastomosis of the large intestine; includes large-to-small and small-to-large bowel anastomosis)
- d) **Bariatric procedures**
- e) **Gastric surgery** (Incision or excision of stomach; includes subtotal or total gastrectomy)
- f) **Spleen surgery**
- g) **Rectal surgery**

4. Exploratory laparotomy (abdominal operations not involving the gastrointestinal tract or biliary system; includes diaphragmatic hernia repair through abdominal approach)

5. Neck surgeries

- a) Thyroid and/or parathyroid surgery
- b) Sialoadenectomy
- c) Major excision or incision of the larynx and radical neck dissection

6. Thoracic surgeries

- a) Heart transplant

7. Neurosurgery

- a) **Laminectomy** (Exploration or decompression of spinal cord through excision or incision into vertebral structures)

8. Urological surgeries

- a) **Kidney transplant**
- b) **Kidney surgery** (Resection or manipulation of the kidney with or without removal of related structures)
- c) **Prostate surgery** (Suprapubic, retropubic, radical, or perineal excision of the prostate; does not include transurethral resection of the prostate)

9. OB&GYN

- a) Cesarean section
- b) Abdominal hysterectomy
- c) Ovarian surgery
- d) Vaginal hysterectomy

(3) Excluded surgeries

1. Anal surgeries

2. Surgery for infected wounds

- a. Debridement for necrotizing fasciitis
- b. Laparotomy for intra-abdominal abscess

3. Breast surgery

Excision of lesion or tissue of breast including:

- a) Radical, Modified, or Quadrant resection.
- b) Lumpectomy.
- c) Incisional biopsy.
- d) Mammoplasty

4. Cardiac surgery

- Procedures on the heart; includes valves or septum

5. Coronary artery bypass graft with both chest and donor site incisions

6. Coronary artery bypass graft with chest incision only

7. Pacemaker surgery

8. Craniotomy

- Excision, repair or exploration of the brain or meninges

9. Spinal fusion

- Spinal fusion or refusion - Immobilization of spinal column

10. Open reduction of fracture

- Open reduction of fracture or dislocation of long bones with or without internal or external fixation

11. Herniorrhaphy

- Repair of inguinal, femoral, umbilical, or anterior abdominal wall hernia

12. Hip prosthesis

13. Knee prosthesis

14. Peripheral vascular bypass surgery

15. Ventricular shunt

(4) Clavien-Dindo classification system:

Grades	Definition
Grade I	Any deviation from the normal postoperative course without the need for pharmacological treatment or surgical, endoscopic and radiological interventions Allowed therapeutic regimens are: drugs as antiemetics, antipyretics, analgesics, diuretics and electrolytes and physiotherapy. This grade also includes wound infections opened at the bedside.
Grade II	Requiring pharmacological treatment with drugs other than such allowed for grade I complications. Blood transfusions and total parenteral nutrition are also included.
Grade III	Requiring surgical, endoscopic, or radiological intervention
- IIIa	Intervention not under general anesthesia
- IIIb	Intervention under general anesthesia
Grade IV	Life-threatening complication (including CNS complications) * requiring IC/ICU-management
- IVa	Single organ dysfunction (including dialysis)
- IVb	Multiorgan dysfunction
Grade V	Death of a patient

(5) Outpatient clinic follow-up form:

Surgical Site Infection (SSI)		
Superficial incisional SSI (SIP, SIS)		
Element	Element Met	Date
Must meet the following criteria:		
Date of event occurs within 30 days after any NHSN operative procedure (where day 1 = the procedure date)		
AND		
Involves only skin and subcutaneous tissue of the incision		
AND Patient has at least one of the following:		
a. Purulent drainage from the superficial incision.		
b. Organisms identified from an aseptically-obtained specimen from the superficial incision or subcutaneous tissue by a culture or non-culture based microbiologic testing method, which is performed for purposes of clinical diagnosis or treatment (for example, not Active Surveillance Culture/Testing (ASC/AST)).		
c. Superficial incision that is deliberately opened by a surgeon, physician* or physician designee AND Culture or non-culture based testing of the superficial incision or subcutaneous tissue is not performed AND Patient has at least one of the following signs or symptoms: 
 • Localized pain or tenderness • Localized swelling • Erythema • Heat 		
d. Diagnosis of a superficial incisional SSI by a physician* or physician designee.		
*The term physician for the purpose of application of the NHSN SSI criteria may be interpreted to mean a surgeon, infectious disease physician, emergency physician, other physician on the case, or physician's designee (nurse practitioner or physician's assistant).		
Comments:		
There are two specific types of superficial incisional SSIs:		

 1. Superficial Incisional Primary (SIP) – a superficial incisional SSI that is identified in the primary incision in a patient that has had an operation with one or more incisions (for example, C-section incision or chest incision for CBGB) 2. Superficial Incisional Secondary (SIS) – a superficial incisional SSI that is identified in the secondary incision in a patient that has had an operation with more than one incision (for example, donor site incision for CBGB) 		
Reporting Instructions for Superficial SSI:		
The following do not qualify as criteria for meeting the NHSN definition of superficial SSI:		

 • Diagnosis/treatment of cellulitis (redness/warmth/swelling), by itself, does not meet criterion "d" for superficial incisional SSI. Conversely, an incision that is draining or that has organisms identified by culture or non-culture based testing is not considered a cellulitis. • A stitch abscess alone (minimal inflammation and discharge confined to the points of suture penetration). • For an NHSN operative procedure, a laparoscopic trocar site is considered a surgical incision and not a stab wound. • A localized stab wound or pin site infection is not considered an SSI; depending on the depth, these infections might be considered either a skin (SKIN) or soft tissue (ST) infection. 		

January 2021

Surgical Site Infection (SSI)		
Deep incisional SSI (DIP, DIS)		
Element	Element Met	Date
Must meet the following criteria:		
Date of event occurs within 30 or 90 days after the NHSN operative procedure (where day 1 = the procedure date) according to the list in Table 2 (see below)		
AND		
Involves deep soft tissues of the incision (for example, fascial and muscle layers)		
AND Patient has at least one of the following:		
a. Purulent drainage from the deep incision.		
b. A deep incision that spontaneously dehisces, or is deliberately opened or aspirated by a surgeon, physician* or physician designee AND Organism(s) identified from the deep soft tissues of the incision by a culture or non-culture based microbiologic testing method which is performed for purposes of clinical diagnosis or treatment (for example, not Active Surveillance Culture/Testing (ASC/AST)) or culture or non-culture based microbiologic testing method is not performed. A culture or non-culture base test from the deep soft tissues of the incision that has a negative finding does not meet this criterion. AND Patient has at least one of the following signs or symptoms: 
 • Fever (>38°C) • Localized pain or tenderness 		
c. An abscess or other evidence of infection involving the deep incision that is detected on gross anatomical or histopathologic exam, or imaging test.		
*The term physician for the purpose of application of the NHSN SSI criteria may be interpreted to mean a surgeon, infectious disease physician, emergency physician, other physician on the case, or physician's designee (nurse practitioner or physician's assistant).		
Comments: There are two specific types of deep incisional SSIs: 
 1. Deep Incisional Primary (DIP) – a deep incisional SSI that is identified in a primary incision in a patient that has had an operation with one or more incisions (for example, C-section incision or chest incision for CBGB) 2. Deep Incisional Secondary (DIS) – a deep incisional SSI that is identified in the secondary incision in a patient that has had an operation with more than one incision (for example, donor site incision for CBGB) 		

(6) Data collection form:

Data collector's details:		
Name:	Study ID:	
Identification details (used locally for follow up only)		
Patient Name:	study ID:	Phone number:
1) Baseline data		

*1-1 Age
  18-25  26-34  35-43  44-52  53-61  62-70  71-79  ≥80	
*1-6 Comorbidities check all that apply)
  Diabetes mellitus  Hypertension  Chronic Kidney Disease  Chronic liver disease  Chronic heart disease  Respiratory Comorbidities:  Asthma  COPD  Anemia  Autoimmune disease  Others comorbid conditions:  Remote infection (Presence of infection in a site other than the site of surgery)	
1-8 *SARS-CoV-2 Details:
 
1-8-1 SARS-CoV-2 infection
  No SARS-CoV-2 infection  Yes –preop diagnosis (at ANY time before surgery) 
1-8-2 How was the SARS-CoV-2 confirmed? (tick all that apply)
  SARS-CoV-2 swab (PCR) test  CT thorax scan  Clinical diagnosis based on history and examination

*1-2 Gender:
  Male  Female	
*Hb A1c level:
 
*Preoperative Cr:
 
*Albumin:
 
*INR:
 
Hb level: if yes specify:
	
1-9 *Medications regularly used :
  Steroids  Iron or other supplements  Chemotherapy  Others:(please specify)

1-3 Height: Weight *BMI:
	
*1-7 ASA:
  Grade 1  Grade 2  Grade 3  Grade 4  Grade 5	

*1-4 Smoking status:
  Yes -current smoker  No -never smoked  No -ex-smoker, stopped ≥ 6 weeks ago  No -stopped in the last 6 weeks	
*1-5 Illicit substance use:
  yes specify:  no	

Data collector's details:		
Name:	Study ID:	
Patient identification details (used locally for follow-up only)		
Patient name:	Study ID:	Phone number:
2) Operative data (Patient's random code:.....)		

2-1 *Date of surgery:
	
2-2 *Hospital admission:
  Performed as day-case (no overnight admission)  Performed with overnight admission (overnight admission can include nights spent in hospital either before and/or after surgery)	
2-3 *Duration of preoperative hospital stay:

2-4 *Type of surgery:
  Emergency  Elective	
2-5 *Surgical procedure:
 
Type of wound: (For definitions please refer to appendix 1 in protocol)
  Clean  Clean-Contaminated  Contaminated  Dirty	
2-6 *Duration of surgery (minutes):

2-7 *Surgical approach:
  Open surgery  Minimally invasive surgery  Minimally invasive surgery converted to open  Hybrid surgery (e.g. laparoscopic abdomen, open chest)	
2-8 *Surgical drain:
  Yes for how many days?  No	
2-9 *wound closure was done by:
  Sutures  staples

Data collector's details		
Name:	Study ID:	
Patient identification details (used locally for follow-up only)		
Patient name:	Study ID:	Phone number:
3) Follow up		

3-1 *Follow up intervals: (Make sure you contact the patient at every interval, then checkmark the interval that the patient develops SSI)
 
 0-7 days  8-14 days  15-21 days  22-28 days  28-30 days
	
3-5 *SSI survey Qs: (check all that apply) Does the patient suffer from....
 
 Pain or tenderness at the surgical site  Swelling at the surgical site  Hotness at the surgical site  Pus draining from the site of incision  Fever postoperatively (degree:)  Surgical incision has been deliberately opened by a physician for signs of infection before due time for stitch removal
 
*if the patient scored 1/6 or more please ask him to directly go to the surgical outpatient clinic to complete the follow up process.
 
*if the patient scored 0/6 please repeat the SSI survey in the mentioned intervals till the end of the 30 days follow up.
	
3-6-1 *Did the patient develop SSI within 30 days postoperatively?
 
 Yes, please specify the postoperative day:  No
 
3-6-2* Was the patient readmitted to the hospital due to SSI?
 
 Yes (for how many days:)  No
 
3-6-3* Did the SSI require another surgical procedure?
 
 Yes (specify:)  No

3-2 *Follow up was done through: (check all that applies)
 
 Inpatient hospital records  Outpatient clinic  Over phone
	
3-7 *Did the patient develop any of the following due to SSI? (check all that apply)
 
 Sepsis  Septic shock  Multiple organ dysfunction syndrome  Wound dehiscence  Others (specify)
	
3-8 *Was there any adverse effect of PVP-I application?
 
 Local skin reaction  Poor wound healing  Other: (please specify:)


3-3 *After surgery the patient was discharged to:
 
 Surgical ward  ICU (for how many days:.....)  Home
	
3-4-1 *What was the length of hospital stay after the surgical procedure?
 
..... days
 
3-4-2 *Was it extended due to wound infection related complications?
 
 Yes (specify:)  No
	
3-9 *Please specify patient grade according to Clavien-Dindo classification
 
 Grade I  Grade II  Grade III  Grade IIIa  Grade III b  Grade IV  Grade IV a  Grade IV b  Grade V
 
*Reason for choosing that grade:

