Patients will be introduced to and asked to participate in the trial when they arrive to the surgical ward or emergency department by the surgical resident. They will not be subjected to any additional steps other than the standard hospital protocols as our trial begins in the operating room where patients will be randomly allocated into 2 groups: the control group (direct wound closure) and the intervention group (PVI wound wash before closure).

After the operation, patients will be monitored and observed at the hospital by the staff until discharge and will be given a specialized follow-up card. Following discharge, follow-up will be in the form of fixed outpatient clinic visit after the first week postoperatively and continue with phone calls made at regular 1-week intervals inquiring about symptoms and signs of SSI based on a questionnaire guided by the CDC definitions [27]. If a patient displays ≥ 1 symptom listed in the CDC checklist (See appendix 5), he/she will be invited to follow-up in our outpatient clinic and will be identified by their card. This will allow the physician to fill out the data collection form in their files and obtain a picture for documentation purposes. Follow-up will continue for a period of 30 days.

Sample Size

Using PASSII program for sample size calculation and assuming SSI incidence of 10% in control group and 5% in intervention group, setting **power** at 80% and **α -error** at 0.05, sample size of 345 patient for each group will be needed. We plan to enroll an additional 10% of the calculated sample size for each group in anticipation of a loss to follow-up rate of 10%. The total sample size will be **760 patients**.

Assignment of Interventions

Sequence Generation

A statistician not directly involved in the study or analysis will prepare a computer-generated randomization sequence. No blocking will be used. The sequence will be provided to the trialists in the form of serially numbered opaque envelopes containing details of either the intervention or the control and a random identifier.

Enrolment and Allocation Concealment

The patients will be enrolled by the resident doctors and given a study ID number.

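### The weekly survey that triggers clinic assessment has no look-back for four of its six items and a narrower opened-incision item than the protocol's own SSI criteria

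*Protocol*

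**What the plan says.** The Outcomes section of the protocol defines the primary outcome cumulatively: "Incidence of superficial and deep surgical site infection (SSI) within 30 days postoperatively".

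Under Participant Timeline, follow-up after discharge is a "fixed outpatient clinic visit after the first week postoperatively and continue with phone calls made at regular 1-week intervals". The trigger for a further clinic visit is also in the present tense: "If a patient displays ≥ 1 symptom listed in the CDC checklist".

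Appendix 6, item 3-5, is the survey used at these contacts. Its stem is "Does the patient suffer from", followed by six items: pain or tenderness, swelling, hotness, pus, postoperative fever, and "Surgical incision has been deliberately opened by a physician for signs of infection before due time for stitch removal". A score of at least 1/6 sends the patient to the outpatient clinic. A score of 0/6 leads only to a repeat of the survey at the next interval.

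Appendix 5 holds the SSI criteria. Superficial criterion c begins "Superficial incision that is deliberately opened by a surgeon, physician* or physician designee". Deep criterion b covers an incision that dehisces or "is deliberately opened or aspirated by a surgeon, physician* or physician designee". Neither is limited by when stitches are due out.

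**The concern.** A screen for a cumulative outcome should ask about everything since the last contact, and should be at least as wide as the definition it serves. Item 3-5 falls short on both counts. Four signs are asked as a state at the call. The item that clearly asks about a past event stops counting once stitch removal is due, although the outcome window runs to day 30.

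Followed as written, a patient can have an event that meets Appendix 5 and not be called in for the assessment at which the physician completes the form. If such events go unrecorded, both SSI rates are too low, the absolute difference shrinks and power is lost. An event that nobody examined is hard to recover later.

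**Working it through.** **Comparison of the texts**

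| Element | Outcome definition (Outcomes; Appendix 5) | Survey trigger (Appendix 6, item 3-5) |
|---|---|---|
| Time frame | Any event to day 30 | Present tense; no look-back for pain, swelling, hotness, pus |
| Fever | A sign under deep criterion b | Postoperative fever; can be read as looking back |
| Opened incision | No stitch-removal limit (superficial c, deep b) | Past event, but only before stitches are due out |
| Physician's diagnosis | Superficial criterion d | No matching item |

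Take a wound that discharges pus on day 16, is opened after stitches were due out or is treated without opening, and is quiet by a call on day 21. Pain, swelling, hotness and pus are negative at the call. The opened-incision item is negative by its own limit, or because the wound was not opened. If there was no fever, the score is 0/6 and the form asks only for a repeat survey. The case does require every other item to be negative at the call.

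The date on which stitches are due out is not defined in the protocol. Item 2-9 records only sutures or staples, so the form does not supply the cut-off.

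**Reproducing the stated sample size**

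Inputs from Sample Size: 10% versus 5%, power 80%, alpha 0.05, 345 per group. With p̄ = 0.075:

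n = [z_α √(2p̄(1−p̄)) + z_β √(p1(1−p1) + p2(1−p2))]² / (p1−p2)²

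One-sided: (1.645 × 0.3725 + 0.842 × 0.3708)² / 0.05² gives 343, close to the stated 345. The two-sided version gives 435. The illustration therefore uses the one-sided test, because it matches the stated 80%. Whether the test should be two-sided is a separate matter.

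**Illustrating the cost of missed events**

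The documents do not give the share missed, so it is assumed, equal in both arms. With n = 345 per group:

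power = Φ{[(p1−p2)√n − z_α √(2p̄(1−p̄))] / √(p1(1−p1) + p2(1−p2))}

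| Share missed (assumed) | Observed rates | Difference (points) | Risk ratio | Power, one-sided | Power, two-sided |
|---|---|---|---|---|---|
| 0% | 10% vs 5% | 5.0 | 0.5 | 80.3% | 70.4% |
| 5% | 9.5% vs 4.75% | 4.75 | 0.5 | 78.3% | 68.0% |
| 10% | 9% vs 4.5% | 4.5 | 0.5 | 76.2% | 65.4% |
| 20% | 8% vs 4% | 4.0 | 0.5 | 71.5% | 60.0% |

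Expected events are 345 × (0.10 + 0.05) = 51.75. Losses of 5%, 10% and 20% remove about 3, 5 and 10 of them.

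**The case against.** Item 3-5 is a referral screen, not the outcome record. Item 3-6-1 asks whether an SSI developed within 30 days and on which day. Item 3-1 asks for the interval in which it developed. Items 3-6-2, 3-6-3 and 3-7 ask about readmission, further surgery and complications of SSI. Inpatient records are a listed source, patients carry a follow-up card, and complications are treated at the trial hospitals at no additional cost. This stands. A reader might infer that a 0/6 score means the event is analysed as SSI-free, or that the trial measures prevalence at the calls rather than 30-day incidence. The documents support neither. What they leave open is how 3-6-1 is answered when every call scores 0/6 and no clinic assessment has followed.

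A reader might also infer that the survey asks only about the moment of the call, or that every treated SSI scores 0/6. Neither is right. The opened-incision item is a past event, the fever item can be read as one, and a wound opened before stitches are due scores at least 1.

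The affected cases may be few. Superficial criterion c itself requires a local sign, and three of its four signs (pain or tenderness, swelling, heat) are in the survey. A recently opened wound will often still be tender. The stitch-removal wording may also be meant only to separate opening for infection from routine stitch removal. That is plausible, but as written the wording excludes a later opening for infection, which Appendix 5 counts.

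Finally, the missed shares are assumptions. Patients and outcome assessors are to be blinded, and nothing in the documents points to different loss between arms. This also stands.

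**Conclusion.** The point holds in a limited form. After the week-1 visit, the scheduled trigger for examination is narrower than the 30-day outcome it serves. Four of six items have no look-back, and the opened-incision item carries a limit that contradicts Appendix 5 (superficial c, deep b). Some SSIs can score 0/6 and not be sent for examination. Other items and records may recover some of them, but the form gives no stated basis for 3-6-1 in a patient who scores 0/6 throughout.

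The size is unknown. If 5% to 10% of SSIs were missed equally in both arms, power would fall by about 2 to 4 points from the stated 80%. That rests on the assumed share, on equal loss, and on the one-sided calculation that reproduces 345. Equal loss leaves the risk ratio at 0.5, so a claim of bias in the relative effect is not supported. The mismatch with Appendix 5 does not depend on any of these assumptions. It should be corrected because the remedy is cheap and events missed during follow-up are hard to recover.

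**What to change.** Make three changes to the follow-up form in Appendix 6:

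1. In item 3-5, delete the stitch-removal limit so that the opened-incision item matches Appendix 5.
2. Word the pus, opened-incision and other sign items as since the last contact (or since surgery, at the first contact), so that a sign that has since settled still counts.
3. Ask item 3-6-1 at every call whatever the score, and have any reported event assessed against Appendix 5.

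The sentence on the clinic trigger in Participant Timeline should be aligned with the same look-back.

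No new scheduled contact is needed. The cost is some extra visits to the existing clinic, mainly from patients reporting ordinary wound pain since the last contact. The documents do not allow that number to be estimated.
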